8.2 Secondary Efficacy Analyses

All secondary efficacy outcome analyses will be performed with the mITT population. All p-values will be two-sided with a significant level set at 0.05.

For all secondary efficacy outcomes the time window is shown in Table A (section 6.2).

8.2.1 Virological evaluation

(a) Proportion of participants with virological failure (2 consecutive VL >50 copies/mL or one VL >50 copies/mL and discontinuation of the study or the study treatment) over 96 weeks

The Kaplan-Meier estimates will be used to determine the proportion of participants with virologic failure, investigated over the 96 weeks. The associated two-sided 95% confidence interval will be calculated for each group with Kalbfleisch and Prentice's formula. The Log-Rank test will be used to compare the virological failure rate between the 2 groups. An additional analysis using Cox regression model with treatment group adjusted for the presence of M184V mutation at baseline and CD4 count at baseline (above versus below 350 cells/ μ L) as well as all other potential confounders will be used to assess the effect of study treatment. We will also calculate the two-sided 95% confidence interval of the difference in the percentage of participants with virological failure (i.e., DTG/RPV failure rate minus the control failure rate) using the following formula (B):

$(\hat{p}_1 - \hat{p}_2) \pm 1.96 \sqrt{\hat{s}_1^2 - \hat{s}_2^2}$ where \hat{s} is the standard error of the proportion calculated with the Kaplan-Meier Method based on the Greenwood pointwise variance estimate.

The time from randomisation to virological failure is defined as the date of the first occurrence of virological failure or the date of last observation for participants without virological failure minus the date of initiating the study treatment. The date of virological failure is the date of the first of the 2 measurements conferring virological failure. The event will be the occurrence of virological failure. Participants in discontinuation for reasons other than virological failure will be censored at the date of last observation before evaluation.

(b) Incidence of genotypic resistance in case of confirmed HIV RNA >50 and baseline factors associated with failure i.e. treatment emergent mutations (NRTI, NNRTI, PI and II regions) as compared with previous resistance tests.

Genotypic resistance testing will be performed in participants with confirmed pVL >50 copies/mL and compared to previous resistance tests. Resistance interpretation will be given by using the Stanford algorithm (<https://hivdb.stanford.edu/hivdb/by-mutations>). The incidence of new resistance mutations will be described and compared between the two treatment groups. The frequency of new mutations conferring resistance to any antiretroviral drug will be given. A table will be built listing all participants with drug resistance mutations by treatment group. The table will include the following information: Patient Id, ARV treatment at baseline, age, sex, CD4 nadir, CD4 count at baseline, CD4/CD8 ratio at baseline, ARV treatment at failure, 1st VL at failure, 2nd VL at failure, resistance mutation at baseline, resistance mutation at failure, drugs resistant at baseline, drugs resistant at failure, drugs concentration at failure.

(c) Proportion of participants with plasma HIV RNA <50 copies/mL at week 24, 48 and 96.

The proportion of participants with plasma HIV RNA <50 copies/mL will be defined as the proportion of participants with HIV RNA <50 copies/mL and no discontinuation of the study or the study treatment. It will be estimated by the number of patients with HIV-RNA<50 copies/mL and no discontinuation at the analysis time point divided by the total number of patients in the mITT population. The associated two-sided 95% exact (Clopper–Pearson) confidence intervals will be calculated for each group as well as the two-sided 95% confidence interval of the difference in the proportion between the two treatment groups. The confidence intervals for the difference in proportions will be calculated with formula (A) defined above. Discontinuation is defined by the discontinuation of the study or any change or modification in the study treatment.

(d) Proportion of participants with plasma HIV RNA <200 copies/mL at week 24, 48 and 96.

The proportion of participants with plasma HIV RNA <200 copies/mL will be defined as the proportion of participants with HIV RNA <200 copies/mL and no discontinuation of the study or the study treatment. It will be estimated by the number of patients with HIV-RNA<200 copies/mL and no discontinuation at the analysis time point divided by the total number of patients in the mITT population. The associated two-sided 95% confidence interval will be calculated for each group as well as the two-sided 95% exact (Clopper–Pearson) confidence interval of the difference in the proportion between the two treatment groups. The confidence intervals for the difference in proportions will be calculated with formula (A) defined above. Discontinuation is defined by the discontinuation of the study or any change or modification in the study treatment.

(e) Change from baseline in cell associated virus using PBMC Illumina sequencing at week 48 and week 96

The evolution of cell associated HIV DNA (based on log transformation) will be described by boxplots for each treatment group at baseline, week 48 and 96. HIV DNA values below the limit of quantification (LOQ) value will be replaced by the LOQ value. The changes from baseline to week 48 and 96 will be compared between the two treatment group using mixed models for repeated measures with random intercept and unstructured covariance matrix, adjusted for baseline value. The models will include treatment group, time, interaction between treatment group and time, and baseline value as covariate. Time will be considered as categorical variable (0, 48, and 96 weeks). Visits window are shown in Table A (section 6.2). Data will be also summarised in tables by mean and standard error.

If the residual of the mixed model is not normally distributed and therefore does not allow the use of parametric test, the changes from baseline to week 48 and 96 of HIV DNA will be compared between the 2 groups using Mann-Whitney-Wilcoxon test.

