3.2 Study endpoints

3.2.1 Primary endpoint/outcome

The primary endpoint is the proportion of participants free of therapeutic failure at week 48 (HIV RNA <50 copies/mL and no discontinuation). Therapeutic failure is defined as virologic failure or discontinuation with HIV RNA <50 copies/mL. Discontinuation is defined by the study follow-up stop or any change or modification in the study treatment regimen.

The following procedure will be used to classify the participants.

1. Virological failure:

- (a) Any patient with HIV RNA levels ≥ 50 copies/mL at any time points will have a repeat test on a second measurement within 2 weeks apart. If the result from the second measurement is <50 copies/mL, the patient will be categorized as HIV-RNA <50 copies/mL. If the result from the second measurement is ≥ 50 copies/mL, the patient will be categorized as virological failure.
- (b) If a patient has HIV-RNA ≥ 50 copies/mL at a given time point and stops the study or at least one drug from the study treatment combination for any reason, he or she will be categorized as virological failure.
- (c) If a patient discontinues the study or at least one drug from the study treatment combination at a given time point because of lack of efficacy then the patient will be categorized as virological failure.

2. Discontinuation (no virological data)

All discontinuations with HIV RNA <50 copies/mL will be considered as no virological data. There are three main reasons for no data at analysis time point:

- (a) Discontinuation due to Adverse Event (AE) or Death.

Any patient who discontinues the study or the study treatment with HIV-RNA is < 50 copies/mL because of AE or death will be classified as discontinuation due to AE or death at from the date of discontinuation.

(b) Discontinuation for Other Reasons.

If a patient discontinues the study follow-up or changes or modifies any drug in the study treatment when his or her HIV-1-RNA is < 50 copies/mL, he or she will be categorized as discontinued for other reasons at from the date of discontinuation.

(c) On study but missing data at analysis time point.

For example, if a participant has no data at analysis time point, but there is an HIV-RNA measurement after the analysis time point, this patient will be considered On Study but with Missing Data at analysis time point.

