3.2.2 Secondary endpoints/outcomes

Secondary endpoints will include secondary efficacy endpoints, secondary safety endpoints, pharmacological endpoints, and secondary endpoints regarding patient related outcomes.

Secondary efficacy endpoints:

- (a) Proportion of participants with virological failure (2 consecutive viral loads > 50 copies at least 2 weeks apart or a viral load > 50 copies/mL followed by a discontinuation of the study or the study treatment), investigated over 96 weeks.
- (b) Incidence of genotypic resistance in case of confirmed HIV RNA > 50 copies/mL and baseline factors associated with failure i.e. treatment emergent mutations (NRTI, NNRTI, PI and II regions) as compared with previous resistance tests.
- (c) Proportion of participants with plasma HIV-1 RNA < 50 c/mL at week 24, 48 and 96.
- (d) Proportion of participants with virological suppression (< 200 copies/ml HIV RNA) at week 24, 48, 96
- (e) Changes from baseline in cell associated virus using PBMC Illumina MiSeq sequencing at week 48 and week 96.
- (f) Changes from baseline in CD4, CD8 and CD4/CD8 ratio over 96 weeks with evaluation at week 24, 48 & 96.

Secondary safety endpoints:

- (g) Number and percentage of participants with adverse events (AEs), severity of AEs, and treatment discontinuations due to AEs.
- (h) Changes from baseline in laboratory parameter at week 24, 48 and 96.
- (i) Changes from baseline in renal markers, bone markers, and fasting lipids at week 24, 48 and 96.

Secondary endpoints regarding pharmacological outcomes:

- (j) Pre-dose plasma concentrations of DTG and RPV at week 4 (experimental arm only), 48 (experimental arm only) & 96. Plus pre/post-dose (as appropriate) at early termination visit and /or in the event of virological failure a post dose sample will be taken within 20-28 hours.

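### The single-value limb of the 96-week virological-failure endpoint is not limited to an unresolved or last on-treatment viral load, conflicts with SAP 3.2.1 and the censoring rule, and has no event date

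*SAP*

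**What the plan says.** The 96-week virological-failure endpoint is defined twice in the SAP, each time with two limbs.

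- **SAP 8.2.1(a):** "2 consecutive VL >50 copies/mL or one VL >50 copies/mL and discontinuation of the study or the study treatment".
- **SAP 3.2.2(a):** two consecutive values above 50 at least two weeks apart, or "a viral load > 50 copies/mL followed by a discontinuation of the study or the study treatment".

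SAP 3.2.1 gives a fuller classification for the primary endpoint.

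- **Rule 1(a), retest of a raised value at any time point:** "If the result from the second measurement is <50 copies/mL, the patient will be categorized as HIV-RNA <50 copies/mL".
- **Rule 1(b), failure by stopping:** it opens "If a patient has HIV-RNA ≥ 50 copies/mL at a given time point and stops the study or at least one drug" of the study combination, and applies whatever the reason for stopping.
- **Rule 2:** "All discontinuations with HIV RNA <50 copies/mL will be considered as no virological data".

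SAP 8.2.1(a) also has a censoring rule: "Participants in discontinuation for reasons other than virological failure will be censored at the date of last observation before evaluation". Its dating rule places the failure at the first of the two measurements that establish it.

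The protocol (6.19) defines virological failure only by two consecutive values above 50 at least 14 days apart. In the primary analysis (protocol 9.2.2), a participant whose repeat test is below 50 is a responder.

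**The concern.** The single-value limb exists to catch a participant who stops with a raised viral load before it can be confirmed. As written it reaches further. It sets no interval between the raised value and the stop, does not restrict the reason for stopping, and does not exclude a value that has since returned below 50. Section 8.2.1(a) joins the two conditions only by *and*, so it does not even fix their order.

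A programmer working from 8.2.1(a) has a complete-looking definition and no pointer to 3.2.1. Coded as written, it can turn stops for adverse events, consent or logistics into virological failures in the Kaplan-Meier estimate, the log-rank test and the Cox model. Few events are expected, so one reclassified participant would be visible. The limb also needs an event date for those analyses, and none is given.

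**Working it through.** **1. The rules side by side**

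The documents give no event count or power for this endpoint, so there is no planned figure to reproduce. Four hypothetical records show where the rules agree and where they part.

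- **A:** week 12 = 70, retest below 50, weeks 24 to 52 below 50, stops at week 60 for an adverse event.
- **B:** the same viral loads, no stop.
- **C:** stops drug at week 30 for an adverse event with viral load below 50, keeps attending, single value of 70 at week 48.
- **D:** last on-treatment value is 70, never retested, then stops.

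| Record | 8.2.1(a), literal | 3.2.2(a), literal | 3.2.1 rules | Censoring sentence, 8.2.1(a) |
|---|---|---|---|---|
| A | Event | Event | Not a failure: 1(a) clears the blip, 1(b) is not met, 2 applies to the stop | Censored: the stop was for another reason |
| B | No event | No event | Not a failure | No stop to censor |
| C | Could be an event | No event: the value came after the stop | Rule 2 applies to the stop | Censored |
| D | Event | Event | Failure, 1(b) | Not applicable |

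A and B have the same virology and differ only in an unrelated stop. A meets both the event definition and the censoring rule in the same section. C can arise because protocol 6.10 and 6.12 ask participants who stop medication to attend visits to week 96. D is the case the limb is needed for. All the rules agree on it, but it has one qualifying measurement and the dating rule requires two, so its date is undefined.

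**2. Size: per-visit model**

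- Blip rate b per visit: 2% to 4%. *Assumed; not in the documents.* All blips resolve.
- Stopping: 15%, spread evenly over 96 weeks. The figure is the expected loss to follow-up in protocol 6.12, used as a proxy.
- Visits at which a blip can precede a stop: weeks 4, 12, 24, 48, 52 and 72 (protocol 6.8, without optional week 60).

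With k visits before the stop, the stop falls in windows of 4, 8, 12, 24, 4, 20 and 24 weeks for k = 0 to 6 (total 96). Spurious events per 100 participants are

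100 × 0.15 × Σ (window ÷ 96) × [1 − (1 − b)^k].

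- b = 2%: sum = 7.018 ÷ 96 = 0.0731, giving **1.10**
- b = 3%: sum = 10.338 ÷ 96 = 0.1077, giving **1.62**
- b = 4%: sum = 13.536 ÷ 96 = 0.1410, giving **2.12**

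**3. Size: per-participant model**

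Extra events = n × P(resolved blip) × 0.15 × share of stops that follow the blip. Arm sizes are 100 and 50 (SAP 5). The blip probability of 2% to 10% per participant and the share of one half to one are assumed.

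- DTG/RPV: 100 × 0.02 × 0.15 × 0.5 = **0.15**, up to 100 × 0.10 × 0.15 × 1 = **1.5**. Chance of at least one: 14% to 78%.
- Control: 50 × 0.02 × 0.15 × 0.5 = **0.08**, up to 50 × 0.10 × 0.15 × 1 = **0.75**. Chance of at least one: 7% to 53%.

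Step 2 gives more because 2% to 4% per visit amounts to a 7.3% to 14.1% chance of an earlier blip among those who stop.

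**4. Difference between arms**

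Suppose stopping is 15% on DTG/RPV and 5% on the control regimen (the 5% is assumed), with b = 3%.

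- If the gap lasted all 96 weeks: (0.15 − 0.05) × 0.1077 = 1.08 points.
- Control participants with virological success switch to DTG/RPV at week 48 (SAP 4.1). If their stopping rate is then the same, only stops before week 48 differ: (8 × 0.03 + 12 × 0.0591 + 24 × 0.0873) ÷ 96 = 0.0317, and 0.10 × 0.0317 = **0.32 points** (0.21 at b = 2%, 0.42 at b = 4%).

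**The case against.** The strongest reply is that the two limbs are shorthand for rules 1(a) and 1(b) of SAP 3.2.1. Those rules sit under a virological-failure heading, rule 1(a) speaks of any time point, and rule 2 answers record A directly. Section 3.2.2(a) at least puts the raised value before the stop, and the censoring sentence points the same way. On that reading only one parenthesis, taken in isolation, misclassifies anyone.

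Much of this stands. It shows what the authors probably meant, and it means misclassification is not a settled consequence of the SAP. It does not close the gap: 3.2.1 is written for the week-48 primary endpoint, the 96-week endpoint carries its own definition in two places, neither refers back to 3.2.1, and no precedence is stated.

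Three stronger inferences are tempting, and the documents do not support them.

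- **That the failure would be dated at the blip.** The dating rule covers only two-measurement failures. The date for this limb is missing, not wrong.
- **That the limb biases the comparison against DTG/RPV by about a point.** That needs an assumed gap in stopping rates lasting all 96 weeks. Allowing for the week-48 switch leaves about a third of a point, still on an assumed control rate.
- **That failures are inflated by a stated percentage.** Dividing step 2's 1.10 to 2.12 by the five non-successes per 100 implied by the 95% planning rate gives 22% to 42%. Those five are a week-48 figure, and under 3.2.1 non-success includes discontinuation and missing data, so they are not a count of 96-week virological failures.

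Protocol 6.19 also asks, where possible, for the rest of a raised sample to be re-analysed before recall. That may remove some assay blips and lower the rates assumed here.

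**Conclusion.** The point holds as an unresolved contradiction and an omission in a secondary endpoint. The literal single-value limb admits a resolved blip followed by an unrelated stop and, in 8.2.1(a), possibly a value taken after stopping. SAP 3.2.1 and the censoring sentence make the resolved-blip case a non-event. Even a proper single-value failure has no event date.

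The likely size is about zero to two participants per 100: 1.1 to 2.1 under the per-visit assumptions and 0.15 to 1.5 under the per-participant ones. Both ranges rest on blip rates that are not in the documents and on the 15% loss figure standing in for unrelated stops. No material between-arm bias is shown. The week-48 primary endpoint has its own rules and is unaffected. The definition should still be settled before the 96-week analysis, because the choice could otherwise be made with the results in view.

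**What to change.** Amend SAP 3.2.2(a) and 8.2.1(a) together, so that the two definitions match:

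1. Limit the single-value limb to participants whose last on-treatment viral load at or before discontinuation is at or above the threshold, with no later value below 50 before the stop.
2. Use one threshold in both limbs, aligned with SAP 3.2.1 (50 copies/mL or more). Both limbs now use above 50, so changing only one would create a new mismatch.
3. State that a value at or above threshold followed by a value below 50 is not an event, and that such a participant is censored at the last HIV RNA if they later stop for another reason.
4. Define the event date for this limb as the date of that last value at or above threshold. Keep the existing rule for two-measurement failures.

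The cost is a few sentences in the SAP and the matching change to the endpoint derivation. No new data are needed.

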3.3 Derived variables

The following derived variables will be studied:

Variables	Calculation method
Age at inclusion, years	Difference between the date of enrolment and the birth date divided by 365.25
CD4/CD8 ratio	CD4 cell count divided by CD8 cell count
Duration on ART, years	Difference between the date of enrolment and the date of first antiretroviral treatment initiation divided by 365.25
Time since HIV diagnosis, years	Difference between the date of enrolment and the date of HIV diagnosis divided by 365.25
Duration of suppressed HIV RNA (<50 copies/mL), year	Difference between the date of enrolment and the date of last detectable viral load (HIV RNA >50 copies/mL) divided by 365.25
Changes from baseline in continuous biological parameters	Difference between value at each time point and the value at baseline
Percent change from baseline in continuous biological parameters	Difference between value at each time point and the value at baseline divided by the baseline value and multiply by 100
Number of potential DDIs avoided	Difference between number of interactions graded "amber or red" before switching and number of interactions graded "amber or red" after switching to dolutegravir/rilpivirine
Total cell associated HIV DNA copies per million PBMC	Total cell associated HIV DNA will be analysed as log transformed, as a continuous variable

[figure not shown]
Partial dates will be extrapolated. For example, all dates saved as NK/FEB/2020 will be recoded as 15/FEB/2020 and those saved NK/NK/2020 will be recoded as 15/JUNE/2020. NK means not known.

4. Study Methods

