6.5 Missing data

In the primary efficacy analysis (FDA Snapshot), participants with missing data at analysis time points will be considered as having lost undetectable plasma HIV-1 RNA levels. The analyses of overall patient disposition will show the number of patients who did not attend each protocol-defined visit.

For all continuous efficacy and safety variables, we will use, in the mITT population, the LOCF (last observation carried forward) approach to deal with missing data. We will also use mixed model as a sensitivity analysis.

For patients reported outcomes, we will use multiple imputation approach to fill in missing data.

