8.2.2 Immunological evaluation

(f) Change from baseline in CD4, CD8, and CD4/CD8 ratio over 96 weeks with evaluation at week 24, 48, and 96.

The evolution of the CD4, CD8 and CD4/CD8 ratio over 96 weeks according to the treatment group will be described by boxplots for each treatment group at each visit. The changes will also be compared between the two treatment group using mixed models for repeated measures with random intercept and unstructured covariance matrix, adjusted for baseline value. The models will include treatment group, time, interaction between treatment group and time, and baseline value. Time will be considered as categorical variable (0, 12, 24, 48, 72 and 96 weeks) according the planned study visits. Visits window are shown in Table A (section 6.2). Data will be also summarised in tables by mean and standard error.

If the residual of the mixed model is not normally distributed and therefore does not allow the use of parametric test, the changes from baseline to week 24, 48 and 96 of CD4 T cell count, CD8 T cell count and CD4/CD8 ratio will be compared between the 2 groups using Mann-Whitney-Wilcoxon test.

9. Safety analyses:

(g) Number and percentage of participants with adverse events (AEs), severity of AEs, and treatment discontinuations due to AEs.

Adverse events (AE), especially grade 3 and 4 AE, serious adverse events (SAE), drug-related AE (all grades), treatment interruption due to AE (all grades), pregnancies and death will be summarized with descriptive statistics. The incidence rates of the events defined above will be compared between the treatment groups using a Poisson regression analysis which accounted for all adverse events and follow-up duration for each participant. The Poisson regression models will include the number of events, the treatment group and the duration of exposure in year in log. The number and percentage of death as well as the causes of death will be given. The number and percentage of pregnant women will also be given. A table will summarize the frequency of adverse events and pregnancies. This table will include the name of event, number and percentage of patients with events, number of events, and incidence rate (IR) per 100 person-years in the DTG/RPV group and the control group respectively, and incidence rate ratio (IRR) and 95%CI for IRR. All grades 3 or 4 AE related to the study drugs and treatment interruption due to AE will be put in the table.

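### The HIV DNA and CD4/CD8 change models include week 0 as an outcome time while adjusting for baseline, so they cannot be fitted or give wrong intervals; SAP 6.5 also ranks LOCF above the mixed model

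*SAP*

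**What the plan says.** SAP 8.2.1(e) sets the HIV DNA comparison as follows: "The changes from baseline to week 48 and 96 will be compared between the two treatment group". The method is "mixed models for repeated measures with random intercept and unstructured covariance matrix, adjusted for baseline value". The fixed effects are then listed: "The models will include treatment group, time, interaction between treatment group and time, and baseline value as covariate". The next sentence gives the levels of time: "Time will be considered as categorical variable (0, 48, and 96 weeks").

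SAP 8.2.2(f) uses the same model for CD4, CD8 and CD4/CD8, with "Time will be considered as categorical variable (0, 12, 24, 48, 72 and 96 weeks) according the planned study visits".

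SAP 3.3 defines change from baseline as "Difference between value at each time point and the value at baseline".

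On missing data, SAP 6.5 says that all continuous efficacy and safety variables will use "the LOCF (last observation carried forward) approach to deal with missing data. We will also use mixed model as a sensitivity analysis". Yet SAP 8.2.1(e), 8.2.2(f), 9(h), 9(i) and 11(o) present the mixed model as the between-arm comparison itself.

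**The concern.** By the definition in SAP 3.3, change at week 0 is exactly zero for every participant. A week-0 outcome row therefore carries no information about treatment, but it does enter the estimates of the baseline slope and the variance. Modelling raw values instead does not help, because the week-0 outcome is then the covariate itself. The stated standard errors, and so the two-sided 0.05 tests announced in SAP 8.2, may be wrong for the HIV DNA and immunological contrasts.

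The LOCF point is separate. With two sections naming different lead analyses, the choice is open until someone makes it, possibly with data in hand. LOCF also suits this design poorly. Controls switch at week 48, so a control participant with no later value would have a pre-switch measurement analysed at week 96 as though taken on DTG/RPV.

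**Working it through.** **Inputs.** Arms of 100 and 50 (SAP 5); two-sided 0.05 (SAP 8.2); change as defined in SAP 3.3; 15% expected loss to follow-up (Protocol 6.12). The documents give no SD, correlation or interval width for these models, so there is no stated figure to reproduce. Assumptions: SD 1 at every visit, no true difference, complete data, and between-visit correlations of 0.4 to 0.9.

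**Reading 1: unstructured covariance across visits.** With baseline slope *b*, the week-0 residual of the change is −*b* times centred baseline, with variance *b*². The log-determinant of the 3×3 HIV DNA residual covariance is 2 ln|*b*| + *c*, where *c* does not depend on *b*. In the scenario run, *c* = −2.46:
- *b* = −0.5: −2.46 − 1.39 = −3.85.
- *b* = −0.00001: −2.46 − 23.03 = −25.49.

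It falls without limit as *b* approaches 0, so the likelihood has no maximum. At *b* = 0 the matrix has rank 2 of 3. Raw outcomes behave the same way as *b* approaches 1. Without week 0 the matrix has full rank (2 of 2).

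**Reading 2: random intercept with one residual variance.** Let *r*(t) be the correlation of visit t with baseline. In large samples:
- The fitted slope *b* is the mean of *r*(t) over the modelled times; week 0 contributes *r* = 1.
- The model's variance per visit is 1 − *b*².
- The true variance of the adjusted value at visit t is 1 + *b*² − 2*b r*(t).
- SE ratio = √[(1 − *b*²) / (1 + *b*² − 2*b r*(t))]; coverage = 2Φ(1.96 × ratio) − 1. Arm sizes cancel.

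The ratio is below 1 exactly when *r*(t) < *b*. Week 0 raises *b*, which is the mechanism of the error.

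Equal correlation 0.6: *b* = (1 + 0.6 + 0.6)/3 = 0.733; model variance 1 − 0.538 = 0.462; true variance 1 + 0.538 − 2(0.733)(0.6) = 0.658; ratio 0.838; coverage 90.0%.

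Decaying correlation 0.8 (week 48) and 0.64 (week 96): *b* = 2.44/3 = 0.813; model variance 0.338; true variances 0.360 and 0.620; ratios 0.969 and 0.739.

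| HIV DNA, times 0/48/96 | Formula: wk 48 / wk 96 | Simulation (4000 runs) |
|---|---|---|
| Equal 0.5 | 90.2 / 90.2% | 90.2 / 90.4% |
| Equal 0.8 | 89.5 / 89.5% | 89.6 / 88.8% |
| Decay 0.5, 0.25 | 93.3 / 88.0% | 92.5 / 87.4% |
| Decay 0.8, 0.64 | 94.3 / 85.2% | 94.6 / 85.2% |
| Decay 0.9, 0.81 | 94.6 / 84.3% | 94.3 / 83.9% |

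If the correlations with baseline are 0.9 and 0.7, then *b* = 2.6/3 = 0.867. Since 0.9 exceeds *b*, the week-48 interval is too wide: ratio √(0.249/0.191) = 1.14, coverage about 97%. At week 96 the ratio is √(0.249/0.538) = 0.68, coverage about 82%.

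**Week 0 removed, random intercept kept.** Under equal correlation *b* = *r*, so the ratio is 1 and coverage is 95%. Under decay 0.8, 0.64: *b* = 0.72; model variance 0.482; true variances 0.366 and 0.597; coverage about 97.5% at week 48 and 92% at week 96. Over the decay patterns simulated, week 96 covers about 89-94% (HIV DNA and CD4 together).

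**CD4 with the SAP's six times.** Equal correlation 0.7: *b* = (1 + 5 × 0.7)/6 = 0.75; ratio √(0.4375/0.5125) = 0.92; coverage 93%. Simulated coverage is 92-93.5% under equal correlation. Under decay it is 92-93% at week 48 and 86-93% at week 96.

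**After the fix.** Visit-wise baseline-adjusted intervals, standing in for an unstructured post-baseline model, cover 94.2-95.8%.

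**LOCF, illustration only.** Assume a true effect of 0.30 SD, correlation 0.8 and one follow-up visit, so that baseline is the value carried. With 15% loss in both arms the expected estimate is 0.85 × 0.30 = 0.255 (simulated 0.256, coverage 92.3%). With more loss on DTG/RPV it is 0.240 (89.8%). Observed data give 0.30 (94.7-95.2%). At 5% loss the effect is small: 0.283, 94.2%.

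**The case against.** **The text may be loose drafting.** The contrasts are named as changes to weeks 48 and 96, so the list containing 0 could be a visit list, and the unstructured matrix could refer to the random effects, which for a lone intercept is one variance. That stands to this extent: a reader might infer that the model must fail to fit, and the SAP supports that only on one reading. But the time list follows the fixed effects directly, the boxplot times are given separately, and the visit-window table in SAP 6.2 has no week-0 row. On the other reading the intervals are still wrong.

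**The direction is not assured.** A reader might infer that every interval is too narrow. This holds under equal correlation; under decay, week 48 can be near nominal or too wide. This stands.

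**Week 0 is not the only cause.** A reader might infer that deleting it restores 95%. Under decay it does not, because the random intercept forces one variance on visits that differ. A random intercept added to a full unstructured residual matrix is also not identifiable, with or without week 0.

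**LOCF.** A reader might infer that carried-forward values will be fed into the mixed model, or that all laboratory contrasts will rest on LOCF. The SAP says neither; it leaves the lead analysis unresolved. Protocol 6.10 and 6.12 ask participants who stop medication to keep attending to week 96, which limits carry-forward. Carrying a pre-switch value to week 96 concerns only controls without a later measurement.

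**Importance.** These are secondary endpoints in a pilot with no formal sample size. The Mann-Whitney-Wilcoxon fallback would avoid the week-0 rows, but it is used only if residuals are judged non-normal.

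**Conclusion.** The point holds for SAP 8.2.1(e) and 8.2.2(f), the two change models that list week 0. The laboratory, lipid, hsCRP and quality-of-life models say only that time is categorical, so the week-0 error cannot be read into them.

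An unstructured visit covariance including week 0 is singular; that needs no assumption beyond SAP 3.3. If a random intercept with one residual variance is meant, nominal 95% intervals for HIV DNA cover about 88-90% at both visits under equal correlation (0.4-0.8). Under decaying correlation they cover about 92-97% at week 48 and 80-87% at week 96. These figures rest on assumed correlations, equal variances and complete data.

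SAP 6.5 conflicts with SAP 8 and 9 on which analysis leads. LOCF does not reach the primary endpoint, where missing counts as failure, or patient-reported outcomes, which use multiple imputation. The primary week-48 result is unaffected. The changes should be made, but nothing here threatens the trial's main conclusion.

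**What to change.** In SAP 8.2.1(e), limit the modelled times to weeks 48 and 96. In SAP 8.2.2(f), limit them to the post-baseline CD4 visits in Protocol 6.8: weeks 24, 48, 72 and 96 (week 12 is in the SAP list but not among those visits). In both, keep baseline as a covariate, delete the random intercept, and specify one unstructured within-participant covariance over the post-baseline visits. A baseline-by-time term is optional. State in the other change models that time means post-baseline visits.

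In SAP 6.5, make the mixed model on observed data the main analysis of continuous efficacy and safety variables, and move LOCF to sensitivity or delete it.

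The cost is SAP wording only, with no new data or visits. Some intervals will be wider.
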